3.4.3 Method of Assigning Participants to Treatment Groups

After obtaining informed consent, participants will receive a screening number and will be screened according to the inclusion and exclusion criteria under provision of an informed consent. Participants who have met all eligibility criteria will receive a participant number upon enrollment in the study (Participant Numbers 101-110). They will receive the participant number just prior to dosing. The participant number will ensure identification throughout the study after study drug administration.

Replacement participants will receive the number of the participant to be replaced, increased by 100 (eg, 201 replacement number for Participant Number 101), and will be administered the same treatment.

Screening failures (defined in Section 3.3.4) and any participants who are eligible for inclusion in the study but do not receive the study drug, will not receive a participant number, and the data obtained will not be recorded in the eCRFs (see Section 5.2.2). For rescreened participants, see Section 3.3.3.

3.4.4 Selection of Doses in the Study

A single 200 mg oral dose of GBT021601 containing ~74 kBq (~2 μ Ci) of [^{14}C]-GBT021601 has been selected to be administered in this study. This dose level has an acceptable safety and tolerability profile in healthy participants (Study GBT021601-011; see Investigator's Brochure for further details)⁸ and is within the anticipated therapeutic range for treatment of SCD.

CCI

[REDACTED]

[REDACTED]

[REDACTED]

Per FDA guidance (May 2022),⁹ the current ADME study should use a dose within the PK linearity range.

A secondary objective of the study is to identify metabolites of ^{14}C -GBT021601 in whole blood, plasma, urine, and feces. The 200 mg dose level of GBT021601 (containing a microtracer amount of ^{14}C -labeled GBT021601) is considered sufficient and necessary to allow for successful GBT021601 metabolite identification. To achieve the necessary analytical sensitivity, both AMS and liquid chromatography will be used for metabolite identification. Although this approach will measure total radioactivity and ^{14}C -labeled metabolites, the presence of nonradiolabeled GBT021601 from the 200 mg dose will be essential to provide sufficient resolution and mass-to-charge of $^{14}\text{C}/^{12}\text{C}$ to identify individual metabolites.

3.4.5 Timing of Doses in the Study

On Day 1, the study drug will be administered as an oral solution under supervision of the Investigator or authorized designee with the participant in the upright position. Study drug will be administered to participants between 08:00 and 11:00 hours in the morning after an overnight fast of at least 10 hours. A light supper will be consumed on the evening before dosing (at least 10 hours before dosing). Fasting will continue for a period of at least 4 hours after drug administration (ie, until scheduled lunch).

During fasting, no fluids are allowed except water; however, water is not allowed from 2 hours predose until 1 hour postdose (apart from the water taken with the dose as described in Section 3.4.1). When not fasting, noncaffeinated fluids are allowed ad libitum.

3.4.6 Meals During the Study

A fasting period of at least 4 hours is required before obtaining clinical laboratory blood samples at all time points.

With the fasting requirements as described in Section 3.4.5 and the restrictions with respect to beverages or food as described in Section 3.4.8.3, there are no special requirements related to food and beverage intake. When not fasting, meals and snacks (such as decaffeinated coffee, herbal tea, fruit, biscuits) will be provided according to the clinical site standard operating procedures (SOPs). A light supper will be provided on the evening before dosing when fasting is required until lunch time.

3.4.7 Blinding

This is an open-label study.

3.4.8 Concomitant Medications and Other Restrictions During the Study

Note: Restrictions that apply to the period before admission to the CRU are described in Section 3.3.1 (inclusion criteria) and Section 3.3.2 (exclusion criteria).

3.4.8.1 Concomitant Medications

The use of all prescribed medication is not allowed from 14 days or 5 half-lives, whichever is longer, prior to dosing (Day 1) until the EoS visit. An exception is made for hormonal contraceptives, which are allowed throughout the study. The use of all over-the-counter medication (vitamin preparations, dietary supplements, or herbal medications such as St. John's wort) is not allowed from 7 days prior to dosing (Day 1) until the EoS visit. An exception is made for paracetamol: from admission onwards, the Investigator may permit a limited amount (eg, up to 2 grams per day) of paracetamol for the treatment of headache or any other pain. Other medication to treat AEs may only be prescribed if deemed necessary by the Investigator. If medication is used, the name of the drug, the dose, and dosage regimen will be recorded in the eCRF.

Receipt of a live vaccine is not allowed within 28 days prior to dosing, and receipt of any other vaccine is not allowed within 7 days prior to dosing.

3.4.8.2 Contraception

Male participants, if not surgically sterilized (eg, vasectomy and azoospermia), are required to use adequate contraception (see description below) and not donate sperm from admission to the CRU [redacted].

Female participants of childbearing potential who have a fertile male sexual partner, are required to use adequate contraception (see description below) from at least 4 weeks prior to dosing (Day 1) [redacted].

Adequate contraception is defined as using hormonal contraceptives or an intrauterine device combined with at least 1 of the following forms of contraception: a diaphragm, a cervical cap, or a condom. Total abstinence from heterosexual intercourse, in accordance with the lifestyle of the participant, is also acceptable.

3.4.8.3 Other Restrictions During the Study

The use of methylxanthine-containing beverages or food (coffee, tea, cola, chocolate, or energy drinks) is not allowed from 48 hours prior to dosing (Day 1) and during confinement in the CRU.

Consumption of grapefruit, grapefruit juice, star fruit, and/or Seville oranges is not allowed from 14 days prior to admission on Day -1 and during confinement in the CRU.

Participants should not consume any foods containing poppy seeds within 48 hours (2 days) prior to each admission to the CRU (including the 24-hour stays) as this could cause a false positive drug screen result.

The use of alcohol is not allowed from 48 hours prior to each admission (including the 24-hour stays) and during confinement in the CRU. The use of drugs of abuse and tobacco and nicotine-containing products is not allowed throughout participation in the study.

Strenuous physical exercise (such as weight training or aerobics) is not allowed within 72 hours (3 days) prior to admission (Day -1), Day 84, and the EoS visit, and during confinement in the CRU, as this could result in abnormal clinical laboratory values. Participants are permitted to exercise after the screening visit until 72 hours prior to admission on Day -1.

Participants are not allowed to donate blood during the study until the EoS visit (other than the blood sampling planned for this study).

3.4.9 Treatment Compliance

To ensure treatment compliance, study drug will be administered in the CRU under supervision of the Investigator or authorized designee. Compliance will be further confirmed by bioanalytical assessment of GBT021601 in whole blood, plasma, urine, and fecal samples (see Section 3.5.4).

The exact time of study drug administration will be recorded in the eCRF. The Investigator or authorized designee will examine the participants to ensure all study drug has been swallowed.

3.5 Pharmacokinetic and Safety Measurements and Variables

3.5.1 Pharmacokinetic and Safety Measurements Assessed and Schedule of Assessments

A schedule of assessments is presented in [Table 1](#).

3.5.1.1 Pharmacokinetic Measurements

Details on sample processing, storage, and shipping of blood, urine, and fecal (and vomitus, if produced) samples will be described in the laboratory manual prepared by ICON.

3.5.1.1.1 Blood Sampling

At the time points defined in the schedule of assessments ([Table 1](#)), blood samples will be taken for the analysis of GBT021601, total radioactivity, and metabolite identification. Blood samples collected up to and including 8 hours postdose will be obtained after the participant has rested at least 5 minutes in the supine position.

The blood samples will be taken via an indwelling intravenous catheter or by direct venipuncture. The exact times of blood sampling will be recorded in the eCRF.

3.5.1.1.2 Urine Collection

During the intervals defined in the schedule of assessments ([Table 1](#)), urine will be collected in urine containers for the analysis of GBT021601 and total radioactivity. Selected pooled urine samples will be used for metabolite identification.

The participants will be instructed to empty their bladders completely before study drug administration and at the end of each collection interval. A blank urine sample will be collected within 12 hours prior to study drug administration. The exact start and end times of urine collection and the urine weight of the entire interval (before and after addition of any urine stabilizers or additives) will be recorded in the eCRF; however the time of each void within the interval may not be recorded.

3.5.1.1.3 Feces Collection

During the intervals defined in the schedule of assessments ([Table 1](#)), feces will be collected for the analysis of total radioactivity. Selected pooled fecal samples will be used for metabolite identification.

Blank fecal sample(s) will be collected within 24 hours prior to admission (ie, 48 hours prior to study drug administration). The exact times of fecal collections and the fecal weight of the entire interval will be recorded in the eCRF.

3.5.1.1.4 Vomitus Collection

If a participant vomits between dosing and 24 hours after administration of the study drug, the vomitus should be collected, if possible. Any collected vomitus will be included in the total radioactivity measurements and in the determination of mass balance.

The exact times and weight of the vomitus produced will be recorded in the eCRF.

3.5.1.2 Safety and Tolerability Measurements

Safety and tolerability assessments will consist of AEs, clinical laboratory, vital signs, 12-lead ECGs, and physical examination. Assessments will be performed in accordance with the schedule of assessments ([Table 1](#)).

3.5.1.2.1 Adverse Events

Adverse events will be recorded from signing the ICF until completion of the EoS/ET visit. Any clinically significant observations, as determined by the Investigator, in results of clinical laboratory, 12-lead ECGs, vital signs, or physical examinations will be recorded as AEs.

A TEAE is defined as any event not present prior to administration of the study drug or any event already present that worsens in either severity or frequency following exposure to the study drug.

An AE that occurs prior to administration of the study drug will be considered a pretreatment AE.

At several time points before and after drug administration, participants will be asked nonleading questions to determine the occurrence of AEs. Participants will be asked in general terms about any AEs at regular intervals during the study. In addition, all AEs reported spontaneously during the course of the study will be recorded. All answers will be interpreted by the Investigator using the most recent version of the MedDRA (ie, Medical Dictionary for Regulatory Activities) for AEs and will be recorded in the eCRF as reported terms.

The Investigator is responsible for evaluating all AEs, obtaining supporting documents, and ensuring that documentation of the event is complete. Details of each reported AE must include, at minimum, severity, relationship to study drug, duration, and outcome. All serious and non-serious AEs must be followed up until they are resolved or stabilized, or until reasonable attempts to determine resolution of the event are exhausted.

The severity of AEs will be graded using the most recent version of the Common Terminology Criteria for Adverse Events (CTCAE; see [Section 8.2.1](#)) 5-point scale: mild (Grade 1), moderate (Grade 2), severe (Grade 3), life-threatening (Grade 4), or death (Grade 5). The relationship between the AEs and the study drug will be indicated as related or not related. Details on rating the severity of AEs and relationship to study treatment are given in [Appendix 8.2](#).

Pregnancy of female participants and female partners of male participants will be monitored along with follow-up, if warranted (see Appendix 8.3).

3.5.1.2.2 Clinical Laboratory

Blood and urine samples for clinical laboratory assessments will be collected, analyzed, and processed according to the clinical site's SOPs. The following parameters will be measured:

- Clinical chemistry (serum quantitatively):
alanine aminotransferase, albumin, alkaline phosphatase, aspartate aminotransferase, bicarbonate, bilirubin (total, direct, and indirect), blood urea nitrogen, calcium, chloride, creatinine, gamma glutamyl transferase, glucose, lactate dehydrogenase, magnesium, phosphorus, potassium, sodium, total protein, and uric acid.
At screening only: creatine phosphokinase and creatinine clearance (glomerular filtration rate, estimated by CKD-EPI).
- Hematology (blood quantitatively):
leukocytes, erythrocytes, hematocrit, Hb, mean corpuscular volume, mean corpuscular hemoglobin, mean corpuscular hemoglobin concentration, platelet count (ie, thrombocytes), RBC count, and white blood cell count, with absolute and percent partial automated differentiation (basophils, eosinophils, lymphocytes, monocytes, and neutrophils). Manual differential white blood cell count differentiation will only be performed if there is an abnormality in the blood cell count in accordance with the clinical site's SOPs.
- Urinalysis (urine qualitatively):
determination of pH and specific gravity, and presence of bilirubin, blood, glucose, ketones, nitrite, protein, leukocytes, and urobilinogen. Urine sediment examinations will only be performed if there is an abnormality in urinalysis in accordance with the clinical site's SOPs.
- Coagulation (blood quantitatively; at screening only):
prothrombin time, activated partial thromboplastin time, and international normalized ratio.
- Serology (at screening only):
hepatitis A virus antibody (total), hepatitis B surface antigen, hepatitis C virus antibody, and human immunodeficiency virus 1 and 2 antibodies.
- Drug and alcohol screen (urine qualitatively):
opiates, methadone, cocaine, amphetamines (including methylamphetamines and ecstasy), cannabinoids, barbiturates, benzodiazepines, nicotine metabolites (cotinine), and alcohol.
- Pregnancy test (females only):
β-human chorionic gonadotropin in serum or urine. If a urine pregnancy test is positive, the result must be confirmed by serum pregnancy test immediately.
At screening only: follicle-stimulating hormone.

Nasal and throat mucosal cell samples will be collected according to the clinical site work instructions. The samples will be tested for SARS-CoV-2 virus using PCR tests as indicated in the schedule of assessments (Table 1), if required by local regulation and guidelines.

In case of unexplained or unexpected clinical laboratory test values, the tests will be repeated as soon as possible and followed up until the results have returned to the normal range and/or an adequate explanation for the abnormality is found. The clinical laboratory will clearly mark all laboratory test values that are outside the normal range, and the Investigator will indicate which of these deviations are clinically significant. Clinically significant laboratory result deviations will be recorded as AEs, and the relationship to the treatment will be indicated (see also Appendix 8.2).

3.5.1.2.3 **Vital Signs**

Systolic and diastolic blood pressure and pulse will be recorded after the participant has been resting for at least 5 minutes in the supine position. These assessments will be made using an automated device whenever possible. Body temperature and respiratory rate will also be measured.

3.5.1.2.4 **Electrocardiogram**

A standard 12-lead ECG will be recorded (in triplicate at screening, and as single ECGs thereafter) after the participant has been resting for at least 5 minutes in the supine position. The ECG will be recorded using an ECG machine equipped with computer-based interval measurements. The following ECG parameters will be recorded: heart rate, PR-interval, QRS-duration, QT-interval, QTcF-interval, and the interpretation of the ECG profile by the Investigator.

3.5.1.2.5 **Physical Examination**

Physical examination will be performed according to the clinical site's SOPs. In addition, body weight and height will be measured according to the clinical site's SOPs. A complete physical examination will be conducted at screening. After screening, physical examinations will be targeted, focusing on specific organ systems, abnormalities identified on the screening examination, and abnormalities related to AEs. Targeted physical examinations will be conducted at the other time points indicated in the schedule of assessments (Table 1). Symptom-directed physical examinations may also be conducted at any time, per the Investigator's discretion.

CCI

A series of black redaction bars of varying lengths, starting from the bottom and moving upwards, with the text 'CCI' in red at the top left.

CCI
[REDACTED]

3.5.1.4 Total Blood Volume

Table 4 presents the number and volume of blood samples and the total volume of blood that is planned to be collected throughout the study per participant.

If deemed necessary by the Investigator or the Sponsor, the number and/or volume of blood samples per assessment may be increased, as long as the total volume of blood drawn for a participant does not surpass 600 mL (except when extra blood samples need to be taken for safety reasons).

Table 4 Number and Volume of Blood Samples and Total Blood Volume Planned to be Collected per Participant

Assessment	Maximum # Samples	Volume of Blood per Sample (mL)	Total Volume of Blood (mL)
PK of GBT021601 in:			
- plasma	30	3	90
- whole blood	30	1	30
PK of total radioactivity in:			
- plasma (predose)	1	10	10
- plasma (postdose)	29	2	58
- whole blood (predose)	1	4	4
- whole blood (postdose)	29	1	29
CCI [REDACTED] [REDACTED]	■	■	■
Metabolite identification (including backup samples) in:			
- plasma	45 22	8	420 176
- whole blood	15 22	4	60 88
CCI [REDACTED]	■	■	■
Clinical chemistry	6	3.5	21
Hematology	6	3	18
Coagulation	1	2.7	2.7
Serology	1	5	5
Total volume of blood drawn			450.7 534.7

PK=pharmacokinetics; CCI [REDACTED]

Note: the blood volumes may be adapted before the start of the study (eg, based on method development or availability of tubes), without exceeding the total amount of 600 mL blood per participant.

3.5.2 Appropriateness of Measurements

The assessments that will be made in this study are standard and generally recognized as reliable, accurate, and relevant.

3.5.2.1 Timing of Assessments

For PK, the predose samples will be obtained within 60 minutes before dosing. Postdose samples up to 20 minutes postdose will be obtained with a time window of ± 1 minute. Thereafter, postdose samples will be obtained with time margins of $\pm 5\%$ of the time that has passed since dosing. The $\pm 5\%$ time window also applies to the start and end times of urine collection intervals and in addition to the total duration of each collection interval.

For safety assessments, predose assessments will be performed between waking up and dosing. For safety assessments up to 2.5 hours postdose, a time window of ± 15 minutes is allowed. Thereafter, serial postdose assessments (eg, multiple assessments within any given day) will be performed with time margins of $\pm 10\%$ of the time that has passed since dosing.

When assessments are planned for the same scheme time, the order of the assessments should be arranged in such a way that PK blood sampling will be done after the ECG and vital signs recordings have been conducted, with PK blood sampling exactly at the scheduled time.

3.5.3 Pharmacokinetic and Safety Variables

3.5.3.1 Pharmacokinetic Variables

Pharmacokinetic variables will be the whole blood, plasma, and urine concentrations of GBT021601, and whole blood, [REDACTED] plasma, urine, and fecal (and vomitus, if applicable) concentrations of [^{14}C]-GBT021601 total radioactivity, and corresponding PK parameters. [REDACTED] The PK parameters

to be determined or calculated using noncompartmental analysis include, but are not limited to, the parameters as given in [Table 5](#). Additional details about the PK analysis and a complete list of PK parameters will be provided in the statistical analysis plan (SAP).

Metabolite identification endpoints, including the structural identification of selected metabolites derived from [^{14}C]-GBT021601 in whole blood and plasma samples, and selected, pooled urine and fecal samples, will be reported separately.

Table 5 Pharmacokinetic Parameters

[¹⁴ C]-GBT021601 Total Radioactivity and GBT021601 in Whole Blood and Plasma	
Parameter	Description
C _{max}	Maximum observed plasma concentration
t _{max}	Time to attain maximum observed plasma concentration
AUC ₀₋₂₄	Area under the plasma concentration-time curve up to 24 hours postdose
AUC _{0-t}	Area under the plasma concentration-time curve up to time t, where t is the last point with concentrations above the lower limit of quantification
AUC _{0-inf}	Area under the plasma concentration-time curve from time 0 to infinity calculated as: AUC _{0-inf} =AUC _{0-t} +C _{last} /k _{el} , where C _{last} is the last measurable plasma concentration
k _{el}	Apparent terminal elimination rate constant (λ_z)
t _{1/2}	Apparent terminal elimination half-life, calculated as 0.693/k _{el}
CL/F	Apparent total clearance, calculated as dose/AUC _{0-inf} (GBT021601 in whole blood and plasma only)
V _z /F	Apparent volume of distribution at terminal phase (GBT021601 in whole blood and plasma only)
AUC B:P	Blood to plasma ratio for total radioactivity and GBT021601 based on AUC
C _{max} B:P	Blood to plasma ratio for total radioactivity and GBT021601 based on C _{max}
CCI	
[¹⁴ C]-GBT021601 Total Radioactivity and GBT021601 in Urine	
Parameter	Description
CL _R	Renal clearance (GBT021601 only)
A _e _{urine}	Cumulative amount of drug excreted in urine at each interval
f _e _{urine}	Fraction of the dose administered excreted in urine (%) at each interval
[¹⁴ C]-GBT021601 Total Radioactivity in Feces (and Vomitus, if Applicable)	
Parameter	Description
A _e _{feces}	Cumulative amount of drug excreted in feces at each interval
A _e _{vomit}	Cumulative amount of drug excreted in vomitus (if applicable)
f _e _{feces}	Fraction of the dose administered excreted in feces (%) at each interval
f _e _{vomit}	Fraction of the dose administered excreted in vomitus (%), if produced
A _e _{total}	Total amount of drug excreted in urine and feces
f _e _{total}	Total fraction of the dose administered excreted in urine and feces

B=blood, P=plasma CCI

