2. OBJECTIVES

2.1 Primary

- To determine the whole blood and plasma concentrations of [¹⁴C]-GBT021601 total radioactivity.
- To assess the mass balance by determining [¹⁴C]-GBT021601 total radioactivity excreted in urine and feces.
- To determine the PK of GBT021601 in whole blood, plasma, and urine.

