3.5.4 Drug Concentration Measurements

Total Radioactivity

The analysis of total radioactivity in whole blood, plasma, urine, and fecal (and vomitus, if produced) samples will be performed by TNO (Zeist, The Netherlands) under responsibility of ICON, using a validated AMS assay. The bioanalytical report(s) for these determinations will be included in the clinical study report (CSR).

The AMS isotope ratio will be converted to ng-eq/mL of whole blood, plasma, urine, or fecal homogenate (and vomitus, if applicable). The total radioactivity concentrations in urine and feces will be used to determine the percentage of dose recovered in urine and feces based upon the radioactive dose administered to each participant.

CCI [REDACTED]

GBT021601

The analysis of GBT021601 in whole blood, plasma, and urine samples will be performed at PPD Bioanalytical Laboratories (Middleton, US) under responsibility of the Sponsor, using a validated liquid chromatography with tandem mass spectrometry assay. The bioanalytical report(s) for these determinations will be included in the CSR.

CCI [REDACTED]

Metabolite Profiling and Identification

Metabolite identification including the structural identification of selected metabolites derived from [¹⁴C]-GBT021601 in whole blood and plasma samples, and selected, pooled urine and fecal samples will be performed by TNO (Zeist, The Netherlands) under responsibility of ICON, and in collaboration with the Sponsor. Pooling of biological samples will be conducted after initial results have been provided to Sponsor. Results will be reported separately from the CSR.

CCI [REDACTED]

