5.1.1 Primary Endpoint

- Concentrations of GBT021601 and of ¹⁴C-GBT021601 total radioactivity in whole blood and plasma
- Amount and fraction of ¹⁴C-GBT021601 total radioactivity dose excreted in urine, feces, emesis (if produced).
- PK parameters of GBT021601 and ¹⁴C-GBT021601 total radioactivity, as feasible, in whole blood and plasma (AUC₀₋₂₄, AUC_{0-last}, AUC_{0-inf}, C_{max}, T_{max}, T_{1/2}, CL_R, CL/F, and V_z/F, if possible, and any other PK parameters as appropriate).
- Distribution of ¹⁴C- GBT021601 total radioactivity in urine and feces.

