16.1.2 Urine, Feces and Vomitus (if applicable) Variables

16.1.2.1 Concentrations

- GBT021601 concentrations and amounts excreted in urine and feces
- ¹⁴C-GBT021601 Total Radioactivity, concentrations and amounts excreted in urine
- 14C-GBT021601 Total Radioactivity, concentrations and amounts excreted in feces
- 14C-GBT021601 Total Radioactivity, concentrations and amounts excreted in vomitus, if applicable.

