16.1.2.3 Excretion Parameters

• PK Parameters for GBT021601 and ¹⁴C-GBT021601 total radioactivity as defined in Table 5.

EDSREP 009 T 01 G Page 15 of 30

Table 5 PK parameters for excretion

Parameter	Description	Analyte
CLR	Renal clearance	GBT021601
Ae _{urine}	Cumulative amount of drug excreted in urine at each interval	¹⁴ C-GBT021601 Total Radioactivity, GBT021601
fe _{urine}	Fraction of the dose administered excreted in urine (%) at each interval	¹⁴ C-GBT021601 Total Radioactivity, GBT021601
Ae _{feces}	Cumulative amount of drug excreted in feces at each interval	¹⁴ C-GBT021601 Total Radioactivity
fe _{feces}	Fraction of the dose administered excreted in feces (%) at each interval	¹⁴ C-GBT021601 Total Radioactivity
Ae _{vomit}	Cumulative amount of drug excreted in vomitus (if applicable)	¹⁴ C-GBT021601 Total Radioactivity
fe _{vomit}	Fraction of the dose administered excreted in vomitus (%), if produced	¹⁴ C-GBT021601 Total Radioactivity
Ae _{total}	Total amount of drug excreted in urine and feces	¹⁴ C-GBT021601 Total Radioactivity
fe _{total}	Total fraction of the dose administered excreted in urine and feces	¹⁴ C-GBT021601 Total Radioactivity

The administered dose is calculated by multiplying the amount (400 mL) of the solution given by the radioactivity per mL of the solution.

The radioactivity per mL solution is calculated by multiplying the label claim (0.185 kBq/mL) by the % radioactivity results (98.5%) of the product (which is established by the QC department):

Administered dose =
$$400 \text{ mL} * 0.185 (kBq/mL) * 0.985 = 72.89 kBq$$

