16.2.4 Pharmacokinetic Amounts Excreted

Individual excretion values will be presented together with descriptive statistics by interval and for each analyte and matrix (ie, urine, feces and total).

Descriptive statistics (number of participants, arithmetic mean, geometric mean, standard deviation, coefficient of variation, median, min, and max) will be used to summarize the amounts excreted for GBT021601 and ¹⁴C-GBT021601 at each scheduled time interval.

EDSREP 009 T 01 G Page 17 of 30

Statistical Analysis Plan GBT2180A-2180AX Protocol: GBT021601-013

Version Date: 01-May-2023

The arithmetic mean values of the cumulative amount excreted in % of the dose in urine, feces and total (urine + feces) versus time (last time point of the interval) will be presented.

Individual plots showing the cumulative amount excreted in % of the dose for all participants versus time (last time point of the interval) in urine, feces and total will be presented.

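### The protocol counts collected vomitus in the mass balance, but Ae_total, fe_total and the plotted total are defined as urine plus feces only

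*Protocol*

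**What the plan says.** The rule for vomitus is in protocol 3.5.1.1.4: "Any collected vomitus will be included in the total radioactivity measurements and in the determination of mass balance".

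Everywhere else, the mass balance total is limited to urine and feces:

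- Protocol 2.1 (repeated in SAP 5.1) states the mass balance objective in terms of "total radioactivity excreted in urine and feces".
- Protocol 3.5.4 says: "The total radioactivity concentrations in urine and feces will be used to determine the percentage of dose recovered in urine and feces".
- Protocol 3.5.3.1, Table 5, defines fe_total as "Total fraction of the dose administered excreted in urine and feces", and Ae_total in the same way.
- SAP 16.1.2.3, Table 5, carries both definitions over unchanged; Ae_total is "Total amount of drug excreted in urine and feces".
- SAP 16.2.4 plots cumulative recovery for "urine, feces and total (urine + feces) versus time".

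Vomitus is not ignored. SAP 5.1.1 names emesis beside urine and feces in a primary endpoint, without defining a combined total. SAP 16.1.2.1 plans "concentrations and amounts excreted in vomitus, if applicable". Both versions of Table 5 include Ae_vomit and fe_vomit, and Listing 16.2.6.2 shows individual vomitus weights and amounts.

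**The concern.** Total recovery is the headline figure of a primary objective. The protocol says that vomitus belongs in the mass balance, yet the only totals defined, in the protocol and in the SAP, leave it out. An analyst who follows Table 5 and one who follows 3.5.1.1.4 would compute different totals for the same participant.

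The fraction is taken over the full administered radioactive dose, so vomited radioactivity stays in the denominator while it is absent from the numerator. A low reported total could then look like incomplete collection or retained drug, when the missing part had in fact been collected, weighed and assayed. The mean recovery figure alone would not show this. A reader would have to rebuild the value from individual results and the listing.

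**Working it through.** **Comparing the definitions.** The question for each place is whether vomitus is in the total.

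| Place | Vomitus in the total? |
|---|---|
| Protocol 3.5.1.1.4 | Yes, in the mass balance |
| Protocol 2.1, SAP 5.1 (objective) | No, urine and feces |
| Protocol 3.5.4 (percentage recovered) | No, urine and feces |
| Protocol Table 5, SAP Table 5 (Ae_total, fe_total) | No, urine and feces |
| SAP 16.2.4 (plotted total) | No, urine + feces |
| Protocol synopsis | Vomitus parameters listed just before the totals; totals not defined |
| SAP 5.1.1 (endpoint) | Emesis named; no total defined |
| Titles of Tables 14.2.2.2 and 14.2.2.4, Figures 14.2.2.5 and 14.2.2.6 | Urine, feces and total; vomitus not named |
| Listing 16.2.6.2 | Vomitus named; a listing, not a total |

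SAP 7.1 lists three changes from the protocol: an added hemoglobin occupancy parameter, the assay schedule for blood, and the TEAE definition. Leaving vomitus out of the total is not among them.

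**Denominator.** SAP 16.1.2.3 gives 400 mL × 0.185 kBq/mL × 0.985 = 72.89 kBq. This reproduces.

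**Size for one participant.** Let f be fe_vomit in percent of dose.

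- Total as defined = fe_urine + fe_feces.
- Total under 3.5.1.1.4 = fe_urine + fe_feces + f.
- The difference is exactly f points, whatever the urine and fecal recovery.

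**Size for the group mean.** With one affected participant among n, the mean falls by f/n. The documents give no emesis rate and no value of f, so the range of 1% to 30% is an assumption.

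| f (% of dose) | Vomitus (kBq) = f × 72.89/100 | Highest possible urine + feces total (%) = 100 − f | Mean shift, n = 8 | Mean shift, n = 10 |
|---|---|---|---|---|
| 1 | 0.73 | 99 | 0.125 | 0.10 |
| 5 | 3.64 | 95 | 0.625 | 0.50 |
| 10 | 7.29 | 90 | 1.25 | 1.0 |
| 20 | 14.58 | 80 | 2.5 | 2.0 |
| 30 | 21.87 | 70 | 3.75 | 3.0 |

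**Side point: the 90% criterion for ending collection.** The protocol glosses excreta as urine and feces. On that reading a participant with f above 10% (7.29 kBq) cannot reach 90%, because at most 100 − f remains. The other two criteria still end collection, so the consequence is possible extra visits and not a biased result.

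**The case against.** The strongest reply is that there is no real conflict. Protocol 3.5.1.1.4 does not mention Ae_total or fe_total. It can be read as requiring that vomitus be assayed, quantified and reported beside urine and feces, which the plan does. The urine-plus-feces total also matches the stated objective. On this reading the request is only for an extra summary.

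The documents leave room for such a summary. Protocol 3.5.3.1 says that its parameter list is not exhaustive, the note closing SAP Table 4 allows additional parameters at the discretion of the PK specialist or sponsor, and SAP 3.0 allows changes without a new SAP version. The table shells are a separate document and may already have a vomitus row. The study is descriptive, the effect is zero by default, and nothing supports the upper end of the assumed range.

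The 90% side point is weak as well. Suppose that all of the dose is excreted at the stated half-life of 28 to 30 days. The first 28 days then hold 1 − 2^(−28/28) = 50% or 1 − 2^(−28/30) = 48%, and the eleven 24-hour stays add about 4%. Collected material would hold about 52% to 54% of dose, so nobody would reach 90%, with or without vomitus, unless interpolated amounts count or radioactivity leaves faster than parent drug.

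Much of this stands: no data are lost, the value can be reconstructed, the effect is contingent, and the 90% point is minor. The central reply does not stand. Permission to report a total with vomitus is not a plan to do so. The protocol leaves the complete parameter list to the SAP, and that list has no such total. A shell row cannot override a written definition. Inclusion in the determination of mass balance asks for more than a separate listing, particularly when Table 14.2.2.4 is titled as total recovery.

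**Conclusion.** The concern holds; the totals are wrong as written. The inconsistency is certain, because it lies in the text, while its numerical effect is conditional. For any participant with collected radioactive vomitus, the reported total is below the mass balance described in protocol 3.5.1.1.4 by exactly fe_vomit points. The effect on the mean, over the range in the table above, assumes one affected participant and an fe_vomit of 1% to 30%; the documents support no particular value. There is no effect if no radioactive vomitus is collected.

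This should be corrected before results are known. It is not a fatal flaw: individual vomitus data are planned and listed. The vomitus formula and the 90% criterion are missing details of lesser weight.

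**What to change.** Keep Ae_total and fe_total as urine plus feces, labelled as such. They match the objective and the aim of describing excretion routes. Then:

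- Add to SAP Table 5 and 16.2.4 a separately labelled total recovery including vomitus, Ae_urine + Ae_feces + Ae_vomit, as an amount and as a percentage of dose.
- If vomitus is collected, show both totals in Tables 14.2.2.2 and 14.2.2.4 and Figures 14.2.2.5 and 14.2.2.6, with a footnote for affected participants.
- Reconcile protocol 3.5.1.1.4 with protocol 2.1, 3.5.3.1 and 3.5.4, and with SAP 16.1.2.3 and 16.2.4.
- As lesser tidying, state in SAP 16.1.2.2 that Ae_vomit is vomitus concentration times vomitus weight, and have the sponsor say whether excreta in the 90% criterion includes vomitus.

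The cost is one parameter pair, one line in 16.2.4, one sentence in 16.1.2.2, and conditional changes to the shells of two tables and two figures. No new data are needed, since vomitus radioactivity and weight are already planned. The SAP can carry the added total, because SAP 3.0 gives it precedence over the protocol's statistical text. Protocol wording is a further step: a clarification memo was used for another point (SAP 7.1), but protocol 4.1 requires ethics committee approval for study changes, so the sponsor must decide which route applies.
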